Modafinil: Use of modafinil involves a minor increase over minimal risk. Modafinil is generally considered to be safe and well tolerated. The most common adverse reactions (5%) associated with modafinil which occurred more frequently than placebo-treated patients in previous clinical trials were headache, nausea, nervousness, rhinitis, diarrhea, back pain, anxiety, insomnia, dizziness, and dyspepsia. It is recommended that caution be used in patients with a history of psychosis, depression, or mania, to avoid exacerbation of these conditions. Serious rash requiring hospitalization and discontinuation of treatment has rarely been reported. Life-threatening skin conditions such as Steven-Johnson Syndrome or Toxic Epidermal Necrosis Syndrome, angioedema, anaphylaxis, hypersensitivity reactions involving multiple organs, new or increased psychiatric symptoms (including worsening depression, mania, depression, suicidality), or increased blood pressure are possible. Dose reduction is recommended in patients with severe hepatic impairment. Modafinil use may decrease the effectiveness of hormonal contraception, use of alternative or concomitant methods of contraception while taking modafinil and for one month after discontinuation of modafinil treatment is recommended. Elimination of drugs that are substrates for CYP2C19 (e.g., phenytoin, diazepam, propranolol, omeprazole, and clomipramine) may be prolonged by modafinil via inhibition of metabolic enzymes, with resultant higher systemic exposure.

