All potential risks of modafinil will be outlined in the informed consent document and discussed with the patient prior to enrollment. Patients will also be advised that there may be unforeseen risks not outlined in the ICF. Based on the package insert, eligibility criteria will exclude pregnant women, and a urine pregnancy test will be required prior to study enrollment. Women of childbearing age will be advised of the risk of decreased effectiveness of hormonal contraception with modafinil use and be advised to use a form of birth control that does not involve hormonal contraception (spermicide or condoms) during the study and for one month after discontinuation of modafinil treatment. Participants with a history of hepatic impairment, participants over age 65, and participants who use warfarin, phenytoin, MAOIs and cyclosporine will be given dose limitations that will not exceed half of the maximal daily dose for healthy patients (50-100 mg once-twice daily as tolerated). Patients will be advised to monitor for common side effects of modafinil including headache, nausea, nervousness, rhinitis, diarrhea, back pain, anxiety, insomnia, dizziness, and dyspepsia while on modafinil, and if these symptoms occur or worsen, to alert the study team, during which time dose reduction or discontinuation will be discussed. Participants who experience worsening depressive symptoms, psychosis, increased suicidality, or suspected allergic reactions (rash, hives, mouth sores, blisters, swelling of the face, eyes, lips, tongue, or throat, trouble swallowing or breathing, fever, shortness of breath, swelling of the legs, yellowing of the skin or whites of the eyes, or dark urine) will be instructed to stop treatment immediately and contact the study team. Participants are also advised not to consume alcohol per the drug label. Participants should be instructed to call study team when new drugs are added or removed from their drug regimens so that drug interactions can be assessed. Participants may choose to discontinue their treatment at any time if they experience any untoward effects that they believe are related to modafinil, but will be encouraged to remain in the study until completion for monitoring. Adverse events and severe adverse events will be assessed/reported regularly and on an as-needed basis in accordance with the protocol, GCP, and IRB standards (see sections 7.5 and 8). Action involving possible PI discontinuation of study drug will be determined promptly in accordance with the protocol, GCP and IRB guidelines, as well as the medical monitor (see section 10 and 13).

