4.2 Exclusion Criteria

1. Current shift work sleep disorder, or narcolepsy diagnosed with polysomnography and multiple sleep latency test (diagnoses in which modafinil is already widely accepted as symptomatic care)
2. History of MS relapse within the last 30 days prior to screening (participants will be considered eligible after the 30-day window);
3. Current stimulant or wake-promoting agent use such as amantadine (Symmetrel), modafinil (Provigil), short or long acting methylphenidate (Ritalin/Concerta), dextroamphetamine (Dexedrine), dextroamphetamine-amphetamine (Adderall, Adderall XR), lisodexamfetamine (Vyvanse), armodafinil (Nuvigil), or amphetamine (Adzenys XR-ODT, Dyanavel XR, and Evekeo) within 30 days of screening (if present, patients could still be eligible after a 30-day washout);
4. For female participants only: Pregnancy or breastfeeding (modafinil is contraindicated in these conditions);
5. For female participants only: Reliance on hormonal contraception (such as birth control pills, shots, implants, patches, vaginal rings) AND concomitant unwillingness to use alternative non-hormonal means of birth control (spermicide or condoms) during the course of the study (modafinil can decrease the effectiveness of oral contraception);
6. Current suicidal ideation (SI) with intent or plan (per a response of ≥ 1 on the suicide item from the Patient Health Questionnaire-9); these individuals will be assessed by a study psychologist and referred for urgent mental health treatment† (people with SI but no intent or plan will be included).
7. Known hypersensitivity to modafinil or armodafinil or its inactive ingredients.
8. History of the following cardiovascular conditions: recent myocardial infarction (last 6 months prior to screening), unstable angina, left ventricular hypertrophy, mitral valve prolapse, NYHA class III or IV congestive heart failure
9. Diagnosis of hypertension within the past year not managed by a health care provider
10. Recent history (within 1 year) of prescription or illicit stimulant abuse (such as cocaine, amphetamine, methamphetamine)
11. Any other medical, neurological, or psychiatric condition that, in the opinion of the investigators, could affect participant safety or eligibility.

†Participant behavior or comments that suggest imminent threat will prompt immediate 911 activation. Behavior or comments that suggest SI with plan but no immediate threat will prompt psychiatric ER referral

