Working with thoughts (part 2) - Challenging unhelpful thoughts, evidence gathering, alternative thoughts; relaxation practice; energy management check-in
Managing emotions - Emotions and fatigue, living in the present, nurturing positive emotions, gratitude, guided imagery; energy management check-in
Building resilience and moving forward - Designing a personal fatigue self-management plan, skills relapse prevention, building resilience
Two 15-20 minute calls between weeks 8-12, to review and troubleshoot implementation of fatigue self-management skills, including their personal self-management plan.

Modafinil: Modafinil will be prescribed by one of the neurologists on the study team. Modafinil (2-[(diphenylmethyl) sulfinyl]acetamide) is a centrally-acting oral agent that is FDA-approved to improve wakefulness in patients with excessive sleepiness associated with narcolepsy, obstructive sleep apnea, or shift work disorder. The mechanism(s) through which modafinil promotes wakefulness is unknown. Modafinil's benefits for fatigue in MS have been demonstrated in 5 previous studies. Three successful open label studies that used various subjective fatigue measures, demonstrated a benefit of modafinil on fatigue intensity. A single-blind placebo-controlled study also demonstrated a significant improvement in fatigue intensity with modafinil in a recent study. One 8-week double-blind placebo-controlled trial which examined the effects of modafinil on fatigue intensity showed a significant improvement in fatigue with modafinil.

Modafinil will be dispensed for Group 2 and 3 patients following 1 week of baseline actigraphy monitoring and at 8 weeks. At baseline, participants will be prescribed the 100 mg pills (enough to take up to 4 pills per day). They will be advised to take 100 mg once a day (upon awakening) as a starting point for the first week. Depending on results, participants will be allowed to adjust their dose based on the following scenarios:

- If the 100 mg/day dose effectively treats their fatigue throughout the day, participants will remain on this dose.
- If the 100 mg/day dose is adequate, but of insufficient duration, participants will be allowed to take another half pill or full pill around lunchtime (early afternoon: at least 8 hours before bedtime) for a total dose of 150 mg or 200 mg a day.

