- If the 100 mg/day dose provides insufficient relief of fatigue, participants may increase the dose to 200 mg/day (upon awakening).
- If the 200 mg/day dose is adequate, but of insufficient duration, participants will be allowed to take another 1 or 2 pills around lunchtime (early afternoon: at least 8 hours before bedtime) for a total dose of 300 mg or 400 mg a day (max dose = 400 mg per day).
- If the 100 mg dose is perceived by the participant to be helpful with fatigue, but associated with excessive side effects (see 1.3), participants will be allowed to decrease their dose to 50 mg, once or twice daily, depending on duration of effect. A pill cutter will be provided by the study team if necessary.

*Participants who report a history of liver problems, participants age 65 or older, participants who use warfarin, phenytoin, MAOIs or cyclosporine†, and participants in whom the investigators think could be at increased risk for side effects, will only be permitted to take ½ of the maximum daily dose, prescribed enough pills to take a maximum of 1 pill twice a day (200 mg/per day) unless they have previously tolerated and required a higher dose prior to enrolling (in which case they will be allowed to return to their previously tolerated dose, up to 400

mg per day) . At baseline, these participants will be prescribed the 100 mg pills. They will be advised to take 50 mg once a day (upon awakening) as a starting point for the first week (A pill cutter will be provided by the study team if necessary.). Depending on results, participants will be allowed to adjust their dose based on the following scenarios:

- If the 50 mg/day dose effectively treats fatigue throughout the day, participants will remain on this dose.
- If the 50 mg/day dose is adequate, but of insufficient duration, participants will be allowed to take another ½ pill around lunchtime (early afternoon: at least 8 hours before bedtime) for a total dose of 50 mg twice a day.
- If the 50 mg/day dose provides insufficient relief of fatigue, participants may increase the dose to 100 mg/day (upon awakening).
- If the 100 mg/day dose is adequate, but wears off more quickly than desired, participants will be allowed to take another half pill or full pill around lunchtime (early afternoon: at least 8 hours before bedtime) for a total dose of 150 mg or 200mg a day (max dose = 200 mg per day).

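### Section 1.3 caps higher-risk participants at half the maximum modafinil dose (200 mg/day) without exception, but the dosing rule in section 5.3 lets some of them take up to 400 mg/day

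*Combined protocol and SAP*

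**What the plan says.** Section 1.3 (Safety, Modafinil) names a higher-risk group: people with a history of hepatic impairment, people over 65, and users of cyclosporine, MAOIs, phenytoin or warfarin. It says that their dose limits "will not exceed half of the maximal daily dose for healthy patients (50-100 mg once-twice daily as tolerated"). No exception is given, and the section does not refer the reader to 5.3 for dosing. The same section says of the drug generally: "Dose reduction is recommended in patients with severe hepatic impairment".

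Section 5.3 (Interventions, Modafinil) covers essentially the same group. It sets the lower age limit at 65 rather than above 65, and adds anyone the investigators judge to be at increased risk. The default is again half the maximum, taken as one 100 mg pill twice a day, but it applies "unless they have previously tolerated and required a higher dose prior to enrolling". For those people, "they will be allowed to return to their previously tolerated dose, up to 400" mg per day. A titration list for the higher-risk group follows. It starts at 50 mg once daily and its last step ends at "max dose = 200 mg per day", with no mention of the exception.

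Section 4.2, criterion 3, excludes current modafinil use, but "if present, patients could still be eligible after a 30-day washout".

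**The concern.** The two sections give different ceilings for the same participant. A 70-year-old earlier user who returns to 300 mg/day complies with 5.3 and exceeds the limit in 1.3. Section 1.3 is where an ethics board or a monitor would look for the limit that protects vulnerable participants, and it is worded as a firm commitment.

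The exception also has no lower bound on liver function. As written, a person with severe hepatic impairment who once needed and tolerated a larger dose could return to the full ordinary maximum, although 1.3 recommends the opposite direction for that condition.

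What is at stake is the accuracy of a stated safety limit and the dose allowed to a few participants. The trial's inference is not affected.

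**Working it through.** No sample size or error-rate formula applies. The check is a comparison of dose ceilings, followed by the question of whether anyone can fall under the exception.

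**Inputs**
- Ordinary maximum, section 5.3: 400 mg/day.
- Higher-risk cap, section 1.3: half of the maximum, also expressed as 50–100 mg taken once or twice daily.
- Higher-risk default, section 5.3: one 100 mg pill twice a day.
- Exception, section 5.3: up to 400 mg/day.

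**Step 1. Reproduce the section 1.3 cap.** The figure 200 mg/day is not printed there but follows in two ways: 400 / 2 = 200 mg/day, and 100 mg × 2 = 200 mg/day.

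**Step 2. Compare with the section 5.3 default.** 1 pill × 100 mg × 2 = 200 mg/day. The defaults agree.

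**Step 3. Compare with the section 5.3 exception.** The excess over the cap is up to 400 − 200 = 200 mg/day, and the ratio is up to 400 / 200 = 2.0. In pills this is four rather than two a day. It is the ordinary maximum for other participants, not a dose outside the protocol's range.

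**Step 4. Can the exception apply to anyone?** Yes.
- Section 4.1 sets no upper age limit.
- Section 4.2 does not list liver history or the four interacting drugs or drug classes as exclusions.
- Criterion 3 admits modafinil users after a 30-day washout.

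The hepatic, over-65 and interacting-drug categories appear in both 1.3 and 5.3, so the mismatch concerns the same people.

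**Step 5. Does another section reconcile the two ceilings?** None does. The safeguards that bear on risk are:
- Prescribing (5.3): "Modafinil will be prescribed by one of the neurologists on the study team".
- Screening (6.1): liver history is taken, and a neurologist assesses eligibility.
- Discretionary exclusion (4.2, criterion 11): "Any other medical, neurological, or psychiatric condition that, in the opinion of the investigators, could affect participant safety or eligibility".
- Notice to the prescribers of interacting drugs (5.3, dagger note). This does not reach participants who are higher-risk through age or liver history.
- Reporting of drug changes to the study team (1.3).
- Extra adverse event reviews at 2–4 and 7–10 days after starting modafinil (6.9). If an excepted participant starts at 50 mg for the first week, the first review falls before any increase and the second at about the time of the first one. The next scheduled review is Week 8.
- Medical monitor input (10.2), and stopping and half-dose re-challenge rules (13). These act once a problem has appeared.

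These reduce the risk, but none aligns the text of 1.3 with that of 5.3.

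**Step 6. How many participants?** The documents give no figure for earlier modafinil use among higher-risk patients, so no count can be computed.

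**The case against.** The strongest reply is that 5.3 is plainly the operative dosing section and 1.3 is a one-clause summary in a risk narrative. Section 5.3 says who gets 200 mg/day, who may go higher, on what condition and to what limit. This stands: a reader might infer that prescribers are left without a rule, and the documents do not support that. A study neurologist would work from 5.3. It does not rescue 1.3, which still states an unqualified limit that 5.3 does not keep.

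A reader might also infer that 5.3 contradicts itself, because its higher-risk list ends at 200 mg/day. That goes too far. The list reads naturally as the default path, with the exception stated just above it. The fair criticism is only that the last step does not repeat the exception.

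A third tempting reading is that the exception is an error unless the larger dose was tolerated with the same risk factor present, for example after reaching 65 or starting warfarin. That is a clinical choice. The documents give no evidence on whether earlier tolerance carries over, and the exception already asks for both tolerance and need. Severe hepatic impairment is different, because 1.3 speaks to it directly. Even there, the text is a recommendation and not a contraindication, and criterion 11 lets the investigators exclude such a person.

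Finally, it cannot be concluded that participants were told the wrong ceiling. The consent form is not among the documents reviewed.

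**Conclusion.** The point holds as a mismatch between sections 1.3 and 5.3. The safety section promises a ceiling of 200 mg/day for a named higher-risk group, and the dosing section allows some of that group up to 400 mg/day, twice the ceiling. In addition, the exception does not leave out severe hepatic impairment, which sits badly with the dose-reduction recommendation in 1.3.

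The conclusion rests on the text and on simple arithmetic, and needs no outside figure. It assumes only that at least one higher-risk earlier user could enrol, which the eligibility criteria permit. The number affected is unknown, probably small and possibly none. No endpoint, sample size, power or analysis is affected. It is worth correcting because it concerns a stated safety limit and the correction is cheap.

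**What to change.** If the exception is intended, which the wording of 5.3 suggests:
1. State it in section 1.3, with its condition and its 400 mg/day limit.
2. In the last step of the 5.3 higher-risk list, mark the 200 mg/day maximum as applying except to those covered by the exception.
3. Exclude severe hepatic impairment from the exception, in line with the recommendation in 1.3.
4. Use age 65 or older in both sections.

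If the exception was not intended, delete it from 5.3, so that 200 mg/day is the ceiling for the whole group, and align the age wording.

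Either way, check that the consent form, which section 12.2 treats as part of the protocol, matches the rule chosen.

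The cost is a short wording amendment to two sections. The downside of item 3 is that an earlier user with severe hepatic impairment could not return to a dose above 200 mg/day. The downside of deletion is that no higher-risk earlier user could. Design, sample size and analysis stay as they are.

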6. STUDY PROCEDURES

Pre-screening: We will be completing record review & pre-screening (over the phone) questions prior to informed consent procedures in order to evaluate initial study eligibility prior to being scheduled for the screening/baseline visit.

6.1 Screening/Baseline Visit

Depending on state or institutional COVID-19 restrictions at time of screening, baseline visits may be conducted virtually (via video meeting) or in-person. Even when in-person visits are permitted, participants will still be given the option for virtual visits.

For in-person visits, subjects will be seen at one of several UM or UW sites for baseline visit activities, including but not limited to the University of Michigan Taubman Neurology Clinic, Michigan Clinical Research Unit (MCRU), and the UW Medicine Multiple Sclerosis Center.

Informed consent will be obtained by qualified study staff. Inclusion and Exclusion Criteria will be reviewed. For virtual visits, the informed consent will be obtained digitally. See section 7.2.4.

The screening portion of this visit will include confirmation of eligibility via:

- 1) Participant self-report (e.g. FSS, PHQ-3, etc.)
- 2) Demographic information
- 3) Focused medical and surgical history as it relates to multiple sclerosis (subtype, prior disease modifying therapy use, disease duration), fatigue, mood disorders and hepatic issues (for modafinil)
- 4) Medication review

5) Neurologist assessment of eligibility

6) Pregnancy test (For individuals of childbearing age who identify their pregnancy status as unsure)

Eligible subjects will be randomized into one of the 3 study arms & will complete baseline assessments of self-reported fatigue, disability, sleep, exercise, self-efficacy, and other quality of life factors via online Redcap surveys.

6.2 Home monitoring 7-day PRO-Diary application (EMA) – BASELINE AND WEEK 12 ONLY: After completing the above screening/baseline activities, participants will receive instruction on use of the PRO-Diary® accelerometer watch, which the participant will wear during two separate 7-day “home monitoring” periods, at baseline (sent home with watch following baseline visit) and 12 weeks to assess physical activity (objectively measured via accelerometry), AND ecological momentary assessment (EMA) of fatigue intensity, fatigue impact, fatigability (ration of fatigue intensity/accelerometer activity counts), and sleep. See “Assessments” section.

The 7-day monitoring period at 12 weeks will take place at the end of the study treatment interval; so that the home monitoring takes place before participants have discontinued their Modafinil, the assessment will begin approximately one week before the end of treatment for all treatment arms (i.e., home monitoring will *conclude* around 12 weeks post-treatment initiation).

6.3 Randomization

Following collection of baseline assessments, participants will be randomized during the baseline screening visit and assigned treatment.

Randomization Process/Blinding: Subjects who meet criteria I/E criteria will be randomized using computer-based randomization via <http://cscar-randomization.appspot.com/> (1:1:1 randomization) to determine whether they will receive telephone based CBT monotherapy (Group 1, n~100), Modafinil monotherapy (Group 2, n~100), or combination therapy with both treatments (Group 3). Statisticians and study staff who process data (subjects will enter data directly into the database, so no study personnel are directly collecting data) will remain blinded to group allocation for the duration of the study. The subject, PI, co-investigators, study interventionists, and coordinators will not be blinded.

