5. STUDY TREATMENTS

5.1 Allocation to Treatment (see also 6.4)

Randomization Process (see also section 6.3): Participants who meet all Inclusion/Exclusion criteria will be randomized (1:1:1 randomization) to CBT (Group 1, n~100), modafinil (Group 2, n~100), or combination CBT+modafinil after the participant has signed consent and completed the baseline activities.

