6.4 Interventions: see also section 5.3

Participants assigned to modafinil or combination therapy will be encouraged to pick up their first supply of modafinil within 7 days of the baseline visit. For virtual visits, participants will receive their first supply of modafinil by mail.

For those who receive CBT or combination therapy will also be able to schedule their first CBT session with the study team during or shortly after this baseline visit.

Participants will be instructed to start their assigned treatment following the 7-day home monitoring period. All treatments will be given for a total of 12 weeks, and treatments will begin after participants complete their first 7-days of PRO-Diary home monitoring.

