6.6 Assessment Windows

Day 1 (start of Week 1) is designated as the point at which treatment starts; this will be somewhere between 7 and 14 days after the baseline visit where randomization occurred. The treatment window is the 12 weeks between Day 1 and the end of Week 12.

Efforts will be made to ensure that assessments are gathered as close to the target assessment time points (Week 8, Week 12, and Week 24) as possible; however, unexpected circumstances often arise that make data collection at very specific time points difficult. Therefore, we have established the following assessment windows. If a participant is not able to complete the assessment during the designated assessment window, they will be allowed to stay in the study (at the site investigator discretion), completing any later assessments as they are able and willing.

Protocol deviations will be completed for participants completing the assessments out of window, with the exception of the prescreening to screening assessment window. Protocol deviations will not be reported for self-report survey data. Self-reported survey data at the baseline, 8 week, 12 week and 24 week surveys is not being collected to assess safety-related information (e.g., side effects, AEs). As is standard, participants are not required to answer any self-reported survey questions they do not wish to answer, and some participants opt to skip questions/surveys they are not comfortable with. If participants skip a question(s) on the surveys (administered online via REDCap), they will be prompted by REDCap that they have missed a question(s) and they can go back and answer or choose to proceed without answering. We have found that in previous studies, skipping questions is rare, and thus we do not expect it to affect data validity.

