6.9 SCHEDULE OF ACTIVITIES

Study Activity	Baseline (week -1 to -2)	Weeks 1-7**	Week 8	Weeks 9-11	Week 12	Weeks 13-23	Week 24
Demographics	X						
Medical/Surgical History	X		X		X		X
Interview with a Neurologist for assessment of eligibility	X						
Krupp's Fatigue Severity Scale (FSS)	X						
Patient Health Questionnaire-3	X						
Medication review	X		X		X		X
Baseline urine Pregnancy test if applicable	X						
AE/SAE review (all participants)*	X		X		X		X
Randomization	X						
Modafinil dispensing (for Groups 2 and 3)	X		X				
Study Intervention Administration		X	X	X	X		
Treatment adherence			X		X		
Treatment Utilization Patterns (post-intervention)							X
Excess modafinil destruction (if applicable)					X		
Computer-based self-report measures							
Modified Fatigue Impact Scale (MFIS)	X		X		X		X
EDSS self-report	X						
STOP-BANG questionnaire	X						
RLS Index	X						

Epworth Sleepiness Scale	X		X		X		X
Insomnia Severity Index	X						
Sleep Hygiene Index	X		X		X		X
Patient Health Questionnaire-8	X		X		X		X
Generalized Anxiety Disorder-7	X		X		X		X
Brief Pain Inventory	X		X		X		X
Exercise (Godin)	X		X		X		X
PROMIS Self-Efficacy Scale	X		X		X		X
PROMIS Cognitive Function	X		X		X		X
MSQOL54- Quality of Life Subscale	X		X		X		X
NeuroQoL Ability to Participate in Social Roles & Activities	X		X		X		X
Post-Treatment Questionnaire					X		X
Patient Global Impression of Change					X		X
7-day home monitoring (PRO-Diary) measures							
Physical Fatigue Severity (4x/day)	X				X		
Mental Fatigue Severity (4x/day)	X				X		
Physical Fatigue Impact (4x/day)	X				X		
Mental Fatigue Impact (4x/day)	X				X		
Wake up time (1x/day)	X				X		
Bed time (1x/day)	X				X		
Sleep refreshed (1x/day)	X				X		
Rest breaks (1x/day)	X				X		
Cognitive clarity (1x/day)	X				X		
Cognitive speed (1x/day)	X				X		

Pain Severity (1x/day)	X				X		
Daytime physical activity (continuous)	X				X		

* For Modafinil-treated participants in Group 2 and 3, AE/SAE review will be additionally assessed at the following time intervals:

- 2-4 days after starting Modafinil
- 7-10 days after starting Modafinil

**Activities marked Week 1-7 begin after the baseline assessments, which include a 7-day home monitoring period.

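### The baseline EMA/actigraphy week behind every outcome in section 2.2.2 is recorded after open-label randomization, so it is exposed to knowledge of the arm

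*Combined protocol and SAP*

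**What the plan says.** Section 2.2.2 defines the secondary outcomes as changes from baseline to week 12 in fatigue intensity, fatigue impact and fatigability. All are measured with the PRO-Diary, four times a day for seven days at each time point.

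The order of events is given in several places:

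- Section 6.3: "participants will be randomized during the baseline screening visit and assigned treatment". On blinding it says: "The subject, PI, co-investigators, study interventionists, and coordinators will not be blinded".
- Section 6.2: the watch is worn "at baseline (sent home with watch following baseline visit) and 12 weeks to assess physical activity".
- Section 6.6, on Day 1 of treatment: "this will be somewhere between 7 and 14 days after the baseline visit where randomization occurred". Participants have 14 days from the visit to complete monitoring, and three full days are accepted as a minimum.
- Section 6.4: CBT and combination participants "will also be able to schedule their first CBT session with the study team during or shortly after this baseline visit". Modafinil participants are encouraged to collect their first supply within 7 days of the visit. Treatment itself starts only after the monitoring week.

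Three other pieces of text bear on the order:

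- Section 5.1 places randomization "after the participant has signed consent and completed the baseline activities", and section 6.3 opens by placing it after the baseline assessments.
- The section 6.9 footnote says that the Week 1-7 activities "begin after the baseline assessments, which include a 7-day home monitoring period".
- Section 6.1 says: "Eligible subjects will be randomized into one of the 3 study arms & will complete baseline assessments of self-reported fatigue".

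Section 9 does not discuss the timing of the EMA baseline relative to randomization. Nor does it say whether the EMA analyses adjust for that baseline.

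**The concern.** A baseline taken before allocation cannot be influenced by the arm, and that is what makes a comparison of change scores safe. Here the participant rates fatigue on 0-10 scales and wears an activity monitor for a week, already knowing whether CBT, modafinil or both will follow. Expectation, disappointment or early changes in pacing could alter the ratings or the activity counts. Fatigability is a ratio of the two. Completion is voluntary, so knowledge of the arm could also affect who has a usable baseline. If any of this differs by arm, part of the apparent treatment effect on a section 2.2.2 outcome would come from the baseline and not from treatment.

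**Working it through.** **1. Timeline.** Randomization takes place during the baseline visit (6.3). The watch goes home after the visit (6.2), and monitoring is completed within 14 days of it (6.6). Day 1 follows monitoring, 7 to 14 days after the visit (6.4, 6.6). A home week that starts after the visit cannot precede a randomization made at the visit. With no participant blinding (5.2, 6.3) and with CBT booking and drug pick-up arranged around the visit (6.4), the arm is known during the week. The exposed data are all 4 x 7 = 28 scheduled baseline EMA occasions per participant, plus the baseline activity counts, in all three arms.

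**2. Wording.** Section 6.2 uses its phrase for screening and baseline activities to mean the in-visit work done before the watch is introduced. On that reading, section 5.1 and the opening of 6.3 agree with the timeline. The 6.9 footnote counts the monitoring week among the baseline assessments. On its own it says only that treatment follows monitoring, which matches 6.4. It conflicts with the timeline only if its definition is carried into 5.1 or 6.3.

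**3. The plan's own figure.** Section 9.1 gives no figure for the EMA outcomes. Its 92% power concerns MFIS and reproduces: SE = 12 x sqrt(1/100 + 1/200) = 1.470; 5/1.470 = 3.402; power = P(Z < 3.402 - 1.960) = 0.925. This point does not depend on it.

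**4. What would bias a change score.** Let b be the between-arm shift at baseline caused by knowing the arm, and w the matching shift at week 12. Participants are unblinded at both times, so the change-score contrast is off by the net shift d, of size |b - w|. The documents give neither b nor w. The values below are assumptions.

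**5. Type I error, unadjusted change score, 100 vs 100.** SE = sqrt(1/100 + 1/100) = 0.1414 SD of change. Type I error = P(Z > 1.96 - d/SE) + P(Z < -1.96 - d/SE).

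| Assumed net shift d (SD of change) | d/SE | Type I error |
|---|---|---|
| 0 | 0 | 5.0% |
| 0.05 | 0.354 | 6.4% |
| 0.10 | 0.707 | 10.9% |

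If half of a 0.10 shift persists to week 12, d = 0.05 and the rate is 6.4%. If all of it persists, the rate is 5%.

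**6. With baseline adjustment.** Assume that the shift is confined to baseline, that SDs are equal at both times, and that the baseline to week-12 correlation is r. The adjusted contrast is off by r x b. For b = 0.10 outcome SD and r = 0.5, the SD of change is sqrt(2 x 0.5) = 1 outcome SD, so the unadjusted rate is again 10.9%. Adjusted: bias 0.05, SE = sqrt(1 - 0.25) x 0.1414 = 0.1225, ratio 0.408, type I error 6.9%. Over r = 0.4 to 0.7 the rates are 9.9% to 15.0% unadjusted and 6.1% to 10.7% adjusted. Adjustment thus shrinks a baseline-only bias without removing it.

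**The case against.** The strongest reply is that nothing has been shown to go wrong. The week is free of treatment, participants remain unblinded at week 12, and a reporting habit that lasts until then cancels from a change score. That stands. It limits the point to an unprotected baseline and does not remove it, because nothing in the plan ensures that a shift is equal across arms or constant over time.

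Three stronger readings are tempting, and the documents do not support them.

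- A reader might infer that 5.1, 6.3 and 6.9 flatly contradict the operational order. They do not. The text leaves unclear whether baseline includes the monitoring week, and it can be read consistently with 6.6.
- A reader might infer from 6.1 that the primary MFIS baseline also follows randomization. That sentence joins two events without giving a sequence, whereas 6.3, the dedicated section, places randomization after the baseline assessments.
- A reader might infer drug exposure during the baseline week, because 6.4 encourages early pick-up while 5.3 dispenses after monitoring. Sections 6.4, 6.6 and 6.7 all hold treatment until monitoring is over.

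A practical objection also has weight. Section 6.7 starts modafinil the day after monitoring ends, and remote participants receive it by mail. Randomizing after monitoring makes a next-day start impossible for them, and making everyone wait for the 14-day window to close would delay early finishers needlessly. The fix has to allow for both.

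**Conclusion.** The point holds in a limited form. The baseline for every section 2.2.2 outcome is collected after open-label assignment and before treatment, and the analysis plan does not address this. It is a weakness of design that is cheap to correct, not a demonstrated bias. The size and direction of any shift are unknown. The rise from 5% to about 11% applies to an assumed net shift of 0.10 SD of change, 100 per arm, a pairwise comparison and an unadjusted change score. With no differential net shift the rate stays at 5%. The primary MFIS conclusion is untouched under the order in section 6.3.

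**What to change.** **Order of events.** Complete the baseline REDCap surveys and the monitoring week first. Then randomize, or disclose the arm, by phone or video with the existing web tool. Do this as soon as the participant finishes monitoring and no later than day 14 after the visit, whether or not the three-day minimum is met, so that no compliance run-in is created. Only then dispense or mail modafinil and book CBT. Amend 5.1, 6.1, 6.3, 6.4, 6.6 and 6.7 to match. Reword 6.1 so that the surveys clearly precede randomization, and allow Day 1 to fall a few days after randomization for mailing, in place of the next-day start.

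**Participants already randomized at the visit.** Add a sensitivity analysis that compares week-12 EMA outcomes between arms, adjusted for baseline MFIS and without the EMA baseline. Flag anyone whose MFIS cannot be shown to precede randomization. The REDCap audit trail (7.2.2) gives survey times, but the documents do not say whether the separate randomization tool logs its own. State that this analysis removes the post-allocation baseline but not week-12 reporting effects.

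**Cost.** One extra remote contact per participant, a short delay to Day 1, and a few consented people lost before randomization. Consents needed to randomize 330 are 330/(1 - loss), rounded up: 334, 341 or 348 for assumed losses of 1%, 3% or 5%. Section 4.0 expects 340 eligible, so a loss of 3% or more would need slightly more recruitment.

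The sensitivity analysis needs no new outcome data but may be somewhat less precise. Assume equal SDs, an EMA baseline to week-12 correlation r of 0.5 to 0.7, and an MFIS to week-12 EMA correlation m of 0.4 to 0.6. Its SE relative to a change score is sqrt((1 - m^2)/(2(1 - r))), from 0.80 (r = 0.5, m = 0.6) to 1.18 (r = 0.7, m = 0.4). Relative to an EMA-baseline-adjusted analysis it is sqrt((1 - m^2)/(1 - r^2)), from 0.92 to 1.28 for the same pairs.
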